The proposed observational study will evaluate the relationship between measures of psychopathology, disordered eating, and impulsivity, (each assessed preoperatively and in the early postoperative period) and changes in weight and psychosocial status in the first two years after bariatric surgery. Secondary outcomes of prevalence and control of T2D and hypertension, health services utilization, and adherence to antidiabetes and antihypertensive medication will also be assessed. All participants will complete assessments at baseline (before surgery) and at 6, 12, and 24 months follow-up. Secondary aims will examine psychopathology, disordered eating, impulsivity, as well as weight loss, in relation to changes in eating behavior, physical activity, psychosocial status, and substance use in the first two years after bariatric surgery. The study has one specific aim and two secondary aims. Specific Aim 1: To determine the relationship between psychopathology, disordered eating, and impulsivity assessed preoperatively and changes in body weight over the first two years following bariatric surgery. We will determine which individual measures falling under these constructs are important in predicting the relative success of bariatric surgery. We will also examine the relationship of changes in the individual measures (from baseline to 6-months after surgery) on subsequent weight loss. (The study is powered on this aim.) We predict that individual measures of psychopathology, disordered eating, and impulsivity will predict smaller weight losses two years postoperatively. We also predict that smaller changes in measures of impulsivity, psychopathology, and disordered eating within the first 6 postoperative months will be associated with smaller weight losses at postoperative month 24. Secondary Aim 1: To examine the correlation structure among our individual measures, and subsequently will generate and confirm composite measures for the three constructs. Composite measures of psychopathology, disordered eating, and impulsivity will predict smaller weight losses two years postoperatively. We also will estimate the proportion of variance in weight loss accounted for by each composite measure. We predict that confirmatory factor analysis will confirm that our individual measures represent three constructs of psychopathology, disordered eating, and impulsivity. Higher values of these composite measures will in turn predict smaller weight losses at postoperative month 24. Secondary Aim 2: To assess the relationship between baseline measures of interest and postoperative changes in caloric and macronutrient intake, eating behavior, physical activity, and psychosocial status. We predict that participants with greater psychopathology, disordered eating, and impulsivity will report greater caloric intake, less favorable changes in macronutrient intake and eating behavior, participate in less physical activity and report more symptoms of psychosocial distress.

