
The following documents are currently attached to this item:

There are no documents attached for this item.

Deception

Does your project use deception? No

Analysis Plan

Analysis will be conducted using Stata 13.0 (Stata Corporation, College Station, TX). After the completion of quality assurance procedures, descriptive statistics will be summarized for all patients by predictor group (dichotomized). Data screening: Prior to performing analyses, standard data screening/ cleaning procedures will be applied. These procedures will: screen the data for data-entry errors; check for outliers; assess the extent and pattern of missing data; create all summary scores needed for analysis; and check that appropriate assumptions of normality are met. In all analyses, the assumptions underlying the application of all the statistical methods that are used will be examined, principally through the use of standardized residuals, influence diagnostics, and graphical displays. Image processing will include image quality assessment procedures that examine global and region of interest (ROI) based raw and processed temporal signal-to-noise ratio, absolute and relative motion, and signal spike count. Potential outliers will be identified in the cumulative sample by examining quality assessment measures and flagging for further investigation subjects greater than two standard deviations from the mean on any one measure (i.e., behavioral performance, image distortion and artifact, general linear model fit). The purpose of this evaluation is to determine whether the time series is likely valid, and, if so, it will remain. Otherwise it will be corrected, if feasible, or removed from the analysis. The final sample will be examined in a similar fashion to determine whether any subjects warrant data cleaning or require exclusion from the final statistical analysis. Analysis of repeated measures: Our four-session within-subject design will generate multiple outcome measures that belong to the Gaussian family, and we will therefore use standard repeated-measures analysis of variance (ANOVA). Imaging outcomes (perfusion and BOLD) will be modeled using standard voxel-based image analysis techniques (described below) that incorporate random effects. Other outcomes (weight loss, ratings) will be modeled using a linear mixed-effects models framework, using using Stata 13.0 (Stata Corporation, College Station, TX). We could use a population averaged approach such as generalized estimating equations. However, the mixed model approach will provide the flexibility to allow for different error variances for different sessions if necessary. Voxel-based image analysis has limited flexibility, particularly when adding multiple covariates and interaction. When needed, summary values (e.g., mean rCBF, mean BOLD% signal change) extracted from ROIs will be modeled in STATAs mixed-models framework. These models can be extended to include additional explanatory variables (e.g., weight change, heart rate, respirations, age). Primary Aim 1 We will take a mixed models approach. The main interest in this study is the Group x Time interaction, where Group will be a between-subjects factor and Time will be a categorical within-subjects factor. This can be interpreted as population averages (GEE fitting method). Hypothesis 1: We will fit a 2 (Group: Dichotomized Baseline Measures, Low, High) x 3 (Time: change from baseline to month 6, 12 and 24) mixed-effects model for change in weight. Hypothesis 2: We will fit a 2 (Group: Dichotomized difference scores, 6 Month minus Baseline, Low, High) x 2 (Time: change from baseline to months 12 and 24) mixedeffects model for change in weight. In addition, the mixed effects models will include adjustments for surgical procedure, gender, and time since surgery. We recognize that the change in weight could also be associated with effects of several pertinent patient characteristics. To this end, we will consider additional covariates (e.g. sociodemographic variables, comorbidities, medication use, tobacco use, and initial weight). For both hypotheses, we will explore the continuous version of our predictor variables, where in place of Group, we use the real values of the predictor. This yields a difference of slopes with respect to predictor value across time points. Secondary Aim 1 We will use confirmatory factor analysis to verify our expected natural groupings of individual measures into composite measures. We will specify 3 factors and use Varimax rotation. We will assemble composite scores for each of our constructs by summing the standardized score values. We will then standardize the composite score and outcome (change in weight at 24 months). We will estimate the partial correlations (direct and indirect) among individual measures, composites, and outcome in a path analysis as suggested by Figure 1 to estimate the fraction of variance in outcome accounted for by each of the constructs. Secondary Aim 2 The outcomes will consist of (continuous) changes in behavior from baseline. We will use correlation to examine the relationship of baseline impulsivity measures to changes at 6, 12 and 24 months. The exception is changes in diet composition. In this analysis, we will use multivariate regression methods,

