
with a 3 level time (6m, 12m, and 24m) x continuous (change), for the different nutrient categories. Missing data The best approach to handling missing data is not to have any, by establishing procedures that correct missingness as it is happening within sessions, and by robust retention efforts as detailed above. In spite of our best efforts, it is likely that some subjects will not provide complete data, by dropping out of the study, by missing an assessment, or by failing to complete all assessments in a session. We will adopt analysis practices that mitigate the impact of missing data. First, all analyses will be conducted using the intention-to-treat (ITT) principle, in which all available data on all participants are included. This approach minimizes bias if individuals drop out for different reasons. In an obesity treatment study, a participant lost to follow-up may be an informative dropout. As long as the missing at random assumption is not violated, attrition related to observed variables (i.e., informative dropout), is a missing or unbalanced data scenario that can be accommodated by the proposed mixed effects models. Furthermore, sensitivity analyses (e.g. baseline carried forward, as treated analysis, various multiple imputation methods, pattern-mixture models) can be conducted and results can be compared to those found with the mixed models. An additional cause of missing data will be item non-response. In the event of items missing at random on survey measures, missing items will be imputed prior to calculating final scores using conditional means, estimated with an iterated version of Bucks method,142 and implemented using the EM algorithm in conjunction with ordinal logistic regression.

The following documents are currently attached to this item:

There are no documents attached for this item.

Are you conducting research outside of the United States? No

Data confidentiality

- **x** Paper-based records will be kept in a secure location and only be accessible to personnel involved in the study.
- x Computer-based files will only be made available to personnel involved in the study through the use of access privileges and passwords.
- x Prior to access to any study-related information, personnel will be required to sign statements agreeing to protect the security and confidentiality of identifiable information.
- x Wherever feasible, identifiers will be removed from study-related information.

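### Secondary Aim 2 predicts postoperative levels for calories, activity and distress but analyses only raw change, whose correlation with baseline impulsivity can vanish or change sign

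*Combined protocol and SAP*

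**What the plan says.** The Objectives define Secondary Aim 2 in terms of change: "To assess the relationship between baseline measures of interest and postoperative changes in caloric and macronutrient intake, eating behavior, physical activity, and psychosocial status". The prediction that follows is mixed. Higher-risk participants "will report greater caloric intake, less favorable changes in macronutrient intake and eating behavior", and will "participate in less physical activity and report more symptoms of psychosocial distress". Calories, activity and distress are thus worded as levels, macronutrients and eating behavior as changes.

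The Analysis Plan, under Secondary Aim 2, treats every outcome as change: "The outcomes will consist of (continuous) changes in behavior from baseline". The method is correlation: "We will use correlation to examine the relationship of baseline impulsivity measures to changes at 6, 12 and 24 months". Diet composition is the one exception. It goes to multivariate regression "with a 3 level time (6m, 12m, and 24m) x continuous (change), for the different nutrient categories", which is again framed on change. Total calories are read here as staying with the correlation.

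No section names the baseline value of an Aim 2 outcome as a covariate or analyses follow-up values. The relevant adjustment sentence belongs to the weight models of Primary Aim 1, where "we will consider additional covariates (e.g. sociodemographic variables, comorbidities, medication use, tobacco use, and initial weight" are mentioned. The general repeated-measures text says mixed models can take further explanatory variables, but it does not name a baseline term either.

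**The concern.** A raw change score contains the starting level with a minus sign. Someone who eats more before surgery has further to fall. The Background gives reasons to expect this for eating: it links impulsivity to overeating, says surgery physically prevents very large meals, and reports that disinhibition and hunger usually decline afterwards.

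Suppose more impulsive participants eat more before surgery and still eat more afterwards, as the aim predicts for calories. If surgery narrows the gap, they also show the larger fall. Correlating impulsivity with raw change may then give no association, or one that reads as a better response. At stake is whether the aim can recognise data that match its own level-worded predictions.

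**Working it through.** The documents give no effect size, SD, correlation or test level for Secondary Aim 2, so there is no planned figure to reproduce. The check is algebraic, with assumed inputs.

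**Notation.** The outcome is scored so that higher is worse. r_pre and r_post are the predictor's correlations with the outcome before and after surgery, and r is the pre/post correlation of the outcome.

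**Formulas.**
- Correlation with raw change = (r_post × SD_post − r_pre × SD_pre) / √(SD_pre² + SD_post² − 2 × r × SD_pre × SD_post)
- Baseline-adjusted (partial) correlation with the follow-up value = (r_post − r_pre × r) / √((1 − r_pre²)(1 − r²))

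When r_post is positive, the raw-change correlation takes the opposite sign to it if r_pre × SD_pre > r_post × SD_post.

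**Assumed inputs.** SD_pre 700 kcal, SD_post 400 kcal, r = 0.3, r_post = 0.2.

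SD of change = √(490,000 + 160,000 − 168,000) = √482,000 = 694. The sign changes once r_pre exceeds 0.2 × 400/700 = 0.114.

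| r_pre | Raw change | Baseline-adjusted |
|---|---|---|
| 0.3 | (80 − 210)/694 = −0.19 | (0.2 − 0.09)/√(0.91 × 0.91) = +0.12 |
| 0.2 | (80 − 140)/694 = −0.09 | (0.2 − 0.06)/√(0.96 × 0.91) = +0.15 |
| 0.1 | (80 − 70)/694 = +0.01 | (0.2 − 0.03)/√(0.99 × 0.91) = +0.18 |

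**Range over the SD ratio** (SD_post/SD_pre), with r = 0.3 and r_post = 0.2:

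| r_pre | Ratio 0.5 | Ratio 0.7 | Ratio 1.0 |
|---|---|---|---|
| 0.3 | −0.205 | −0.155 | −0.085 |
| 0.2 | −0.103 | −0.058 | 0.000 |
| 0.1 | 0.000 | +0.039 | +0.085 |

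If the spread narrows, equal correlations before and after surgery are enough for a reversal. If the link before surgery is weaker, the result is attenuation without reversal.

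**What a study would report.** Each scenario used 4,000 simulated studies of 300 participants (the accrual target, with no dropout) and two-sided 5% tests. The 5% level is also an assumption. r = 0.3 and r_post = 0.2 throughout.

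| r_pre, SD ratio | Raw change significant, opposite to prediction | Raw change significant, as predicted | Adjusted significant, as predicted |
|---|---|---|---|
| 0.3, 0.5 | 94% | 0% | 56% |
| 0.3, 0.7 | 77% | 0% | 55% |
| 0.2, 0.7 | 17% | 0.2% | 74% |
| 0.1, 0.7 | 0.6% | 10% | 88% |

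**The case against.** The strongest reply is that the aim is declared as change, and the Procedures section also speaks of change in physical activity as the outcome of interest. A larger fall among those who start higher is then a correct answer, not a wrong sign. This stands for macronutrients and eating behavior, where the prediction itself is about changes. It does not settle calories, activity and distress, where the prediction is about levels and no analysis of levels is planned.

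Three stronger readings are tempting but not supported:

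- **That the sign will reverse.** Reversal needs r_pre × SD_pre > r_post × SD_post, and the documents supply none of these quantities. The Background describes levelling for eating only. Nothing shows that surgery narrows the spread of activity or distress.
- **That predictor and outcome come from the same instrument.** A baseline score correlates about −0.50 with its own change when stability is 0.5 and the SDs are equal, and −0.39 to −0.88 over stabilities of 0.3 to 0.7 and SD ratios of 0.5 to 1.0. But the written correlation uses impulsivity measures: stop-signal reaction time, Stroop interference and the discount rate. None is an Aim 2 outcome. The coupling arises only if the method is extended to the disordered-eating predictor in the hypothesis.
- **That raw change should be dropped.** In a non-randomised cohort, change and baseline-adjusted analyses answer different questions, and adjustment is not neutral. With r_pre = 0.3, r_post = 0.1 and r = 0.5, the adjusted correlation is itself −0.06. Baseline intake rests on two 24-hour recalls, so adjusting for it can leave residual bias.

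**Conclusion.** The concern holds in a limited form. For calories, activity and distress, the planned raw-change correlation does not test the level-worded prediction, and data that match the prediction could give a null or opposite-sign result. In the kcal illustration, raw change gives −0.19 to +0.01 where the baseline-adjusted correlation is +0.12 to +0.18. These figures rest wholly on the assumed SDs and correlations. They show what is possible, and the mechanism is best supported for eating. For macronutrients and eating behavior, change answers the stated question, although its size and sign still depend on the starting level. This is a secondary aim on which the study is not powered, so the remedy is a cheap improvement to the analysis text.

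**What to change.** Amend the Secondary Aim 2 text of the Analysis Plan as follows:

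1. State for each outcome whether the target is the postoperative level or the change from baseline.
2. Where it is a level (calories, activity, distress), make the main analysis a regression or mixed model of the 6-, 12- and 24-month values on the baseline predictor, with the baseline value of that outcome as covariate. Report raw change alongside.
3. Where it is a change (macronutrients, eating behavior), keep change and add the baseline-adjusted model as a supporting analysis.
4. If the analysis is extended to the disordered-eating predictor, do not count a correlation between a baseline score and change in the same instrument as evidence for the aim.

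The cost is SAP wording and a little more analysis of data already being collected. Because an error-prone baseline can bias the adjusted result, both results should be shown.

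### The Secondary Aim 2 analysis names only impulsivity as a predictor, so its psychopathology and disordered-eating hypotheses have no specified analysis for most of the aim's outcomes

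*Combined protocol and SAP*

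**What the plan says.** In the Objectives, Secondary Aim 2 is set out as follows: "To assess the relationship between baseline measures of interest and postoperative changes in caloric and macronutrient intake, eating behavior, physical activity, and psychosocial status". The prediction attached to it covers three constructs: "We predict that participants with greater psychopathology, disordered eating, and impulsivity will report greater caloric intake", and it goes on to the other outcomes of the aim.

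In the Analysis Plan, the Secondary Aim 2 paragraph first defines the outcome scale: "The outcomes will consist of (continuous) changes in behavior from baseline". It then gives the method: "We will use correlation to examine the relationship of baseline impulsivity measures to changes at 6, 12 and 24 months". Next comes a carve-out: "The exception is changes in diet composition. In this analysis, we will use multivariate regression methods", described as "with a 3 level time (6m, 12m, and 24m) x continuous (change), for the different nutrient categories". No baseline construct is named in that regression.

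Two other statements bear on the point. The general repeated-measures text says: "Other outcomes (weight loss, ratings) will be modeled using a linear mixed-effects models framework". The Missing data section says that attrition related to observed variables "is a missing or unbalanced data scenario that can be accommodated by the proposed mixed effects models", provided that data are missing at random.

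**The concern.** The aim has three constructs as predictors, and its analysis has one. An analyst who follows the paragraph literally would run the impulsivity tasks against behaviour change and stop there. Hypotheses about the other two constructs would then either go unreported or be added after the data are seen, when they would count as post hoc. Psychosocial status is affected as well. The Abstract and the overall objectives place it beside weight as something that all three constructs are meant to explain.

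The method is also weaker than the one used for Aim 1. The Aim 1 mixed models adjust for surgical procedure, gender and time since surgery. The Secondary Aim 2 correlations carry no stated adjustment. The plan expects dropout, accepts that it may be informative in an obesity study, and looks to its mixed models to deal with it. A separate correlation at each visit does not have that protection.

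**Working it through.** The documents give no figure for this point, so there is none to reproduce. The check is a comparison of text with a count, followed by one formula that bears on the fix.

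**1. Hypothesis against analysis.** Inputs: three constructs and five outcome domains, both from Secondary Aim 2 in the Objectives; methods from the Secondary Aim 2 paragraph of the Analysis Plan. Diet composition is read here as macronutrients only.

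| Outcome domain | Psychopathology | Disordered eating | Impulsivity |
|---|---|---|---|
| Caloric intake | none named | none named | correlation |
| Macronutrient intake | regression, predictor not named | regression, predictor not named | regression, predictor not named |
| Eating behaviour | none named | none named | correlation |
| Physical activity | none named | none named | correlation |
| Psychosocial status | none named | none named | correlation |

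- Pairs in all: 3 × 5 = 15.
- Named analysis: 1 × 4 = 4.
- Undetermined: 3 × 1 = 3.
- No named analysis: 2 × 4 = 8.
- Check: 4 + 3 + 8 = 15.

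If caloric intake also belongs to diet composition, the split is 1 × 3 = 3 named, 3 × 2 = 6 undetermined and 2 × 3 = 6 with none, again 15.

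**2. Does another part of the plan fill the gap?** Primary Aim 1 models change in weight. Secondary Aim 1 uses all three constructs in a path analysis, but its outcome is weight change at 24 months. The general sentence on ratings names no predictor and is not tied to this aim. None of these supplies the missing analyses.

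**3. Adjustment and dropout.** The covariates procedure, gender and time since surgery are attached to the mixed models under Primary Aim 1. The Secondary Aim 2 sentence names none. A correlation at 6, 12 or 24 months uses the participants observed at that visit; this is inferred from the method, since the plan does not say so. It does not borrow from a participant's other visits as a mixed model does.

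**4. Why the correlation should not simply be extended.** The instruments listed under Eating Behavior in the study procedures make up the disordered-eating composite, and eating behaviour is also an Aim 2 outcome. For a measure X with equal variances at baseline (X0) and follow-up (X1) and test-retest correlation ρ:

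corr(X0, X1 − X0) = (ρ − 1)/√(2(1 − ρ)) = −√((1 − ρ)/2)

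- ρ = 0.7: −√0.15 = −0.39
- ρ = 0.5: −√0.25 = −0.50
- ρ = 0.3: −√0.35 = −0.59

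The documents give no test-retest values; 0.3 to 0.7 is an assumed range.

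**The case against.** The strongest reply is that impulsivity in the analysis sentence is a drafting slip. The aim itself speaks of baseline measures generally, and the authors may have meant all three constructs. That is plausible, but it supports a correction: the sentence is the only aim-specific instruction, and an analyst would follow it.

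A second reply is that this is a secondary aim of an observational study powered on Specific Aim 1, where simple correlations may be enough and a preference for adjusted models is partly taste. That has some force on the choice of method. It does not answer the missing predictors.

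Four stronger readings are tempting, and the documents do not support them.

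- A reader might infer that correlation is the only Aim 2 method. It is not, because diet composition has its own regression.
- A reader might infer that the two hypotheses are never tested. The diet regression leaves its predictor open, so for those pairs the position is undetermined. Both constructs are also tested against weight elsewhere in the plan.
- A reader might infer that the correlations are restricted to study completers. The Missing data section says that all available data on all participants are used, so each correlation would include whoever attended that visit.
- A reader might infer that the Missing data section commits every analysis to mixed models. Its statement about all analyses concerns the intention-to-treat principle. The mixed-model sentence refers to the models proposed, and other methods are listed as possible sensitivity analyses.

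Finally, the coupling figures do not describe the plan as written, which correlates impulsivity tasks with changes in other behaviours. They apply only if the same correlation is extended to eating measures against their own change.

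**Conclusion.** Wrong as written, and more than a missing detail: the stated rule for Secondary Aim 2 does not carry out the stated aim. Psychopathology and disordered eating have no specified analysis for 8 of 15 construct-by-outcome pairs, or 6 of 15 on the wider reading of diet composition. A further 3 (or 6) pairs fall under a regression whose baseline predictor is not named; these include impulsivity against macronutrients. The impulsivity analyses that are specified lack Aim 1's adjustment and its missing-at-random protection. The counts rest on taking the five domains as the Objectives list them, and on not reading predictors into sentences that name none. The conclusion is limited to the outcomes of Secondary Aim 2.

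**What to change.** Replace the Secondary Aim 2 analysis wording along these lines:

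- For each Aim 2 outcome, including the nutrient categories, fit a linear mixed model of change at 6, 12 and 24 months with a continuous baseline predictor by visit, adjusted for the Aim 1 covariates (surgical procedure, gender, time since surgery).
- Do this separately for the psychopathology, disordered-eating and impulsivity measures.
- In the diet-composition regression, name these same measures as the baseline predictors.
- Do not test an eating measure, or a composite that contains it, as a predictor of its own change.

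The cost is a change of plan wording and more model runs on data already being collected. The downside is a larger number of secondary tests to report.
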